6.2 Dose Modification

6.2.1 Dose Modification of Fulvestrant

During the study period, dose modifications of fulvestrant are allowed as decided by the treating physician.

6.2.2 Dose Modification of Onapristone

In the preliminary studies, there were no grade 4 adverse effects (AEs) reported with a single dose of onapristone (10 mg immediate release (IR)) in healthy female volunteers. The treatment doses of onapristone (10–50 mg extended release BID or 00 mg /day) in patients with prostate cancer, breast, ovarian and endometrial cancers also demonstrated no grade 4 toxicities. The majority of the adverse toxicities were related to asthenia (16%), GGT increase (15%), nausea (14%), increased AST (12%), and increased ALT (11%). Two subjects discontinued onapristone due to AEs, and one patients discontinued due to unrelated AEs (cytopenias) due to marrow involvement of the disease secondary to bone metastases. One patient had 25% dose reduction due to liver toxicity, and ultimately discontinued onapristone due to diseases progression and LFT abnormalities. One death was reported within 30 days of discontinuation of onapristone due to

respiratory distress related to progressive lung metastases. Based on this available data under the Context Therapeutics development program, no major adverse effects are anticipated from onapristone, and the table below provides additional guidelines for dose modifications.

Management of severe or intolerable adverse reactions at least possibly, probably or definitely related to onapristone requires dose reduction, temporary interruption, and/or discontinuation of onapristone therapy. A maximum of two dose reductions will be allowed, at which point the patient will be allowed to continue treatment at that reduced dose for the following cycles. Any adverse events even after the dose reductions will indicate treatment discontinuation with onapristone. Dose reduction should be based on the worst preceding toxicity. Please refer to Tables 4, and 5 for guidance.

Table 4 Dose Reduction Steps for Onapristone

Dose level	Dose and schedule	Number of tablets and strength
Starting dose	50 mg BID continuously	2 × 20 mg tablet and 1 × 10 mg tablet
Dose level 1	40 mg BID continuously	2 × 20 mg tablet
Dose level 2	30 mg BID continuously	1 × 20 mg tablet and 1 × 10 mg tablet

Recommendations for dose reduction or interruption of onapristone in the management of adverse reactions are summarized in Table 5. Clinical judgment of the treating physician, including confirmation of lab values (by means of retesting as deemed necessary), should guide the management plan of each subject based on individual benefit/risk assessment.

Once the onapristone dose has been reduced, no re-escalation will occur, even upon resolution of the AE. If a subject requires a dose delay of onapristone for > 28 days from the intended day then the subject must be discontinued from onapristone but may continue fulvestrant.

Table 5 Criteria for Dose Modification of Onapristone Treatment

Adverse event	Dose of Onapristone
Hematological*	
Neutropenia (ANC)	
Grade 1 (< LLN - $1.5 \times 10^9/L$)	Maintain dose level.
Grade 2 (< $1.5-1.0 \times 10^9/L$)	Maintain dose level.
Grade 3 (< $1.0-0.5 \times 10^9/L$)	
First occurrence	Dose interruption until $ANC \geq 1.0 \times 10^9/L$; when improved, resume and reduce by one dose level.
Second occurrence	Dose interruption until $ANC \geq 1.0 \times 10^9/L$; when improved, resume and reduce by one dose level.
Third occurrence	Discontinue onapristone and continue fulvestrant at the discretion of treating physician.
Grade 4 (< $0.5 \times 10^9/L$)	Discontinue onapristone and continue fulvestrant at the discretion of treating physician.

Adverse event	Dose of Onapristone
Febrile neutropenia: ANC < $1.0 \times 10^9/L$, with a single temperature of $\geq 38.3^{\circ}C$ or a sustained temperature of $\geq 38^{\circ}C$ for more than one hour.	First or second episode: Dose interruption until resolved until $ANC \geq 1.0 \times 10^9/L$; when improved and afebrile, resume and reduce by one dose level. Third episode of febrile neutropenia: Discontinue onapristone and continue fulvestrant at the discretion of treating physician.
Thrombocytopenia (PLT)	
Grade 1 ($<LLN - 75 \times 10^9/L$)	Maintain dose level.
Grade 2 ($<75-50 \times 10^9/L$)	Maintain dose level.
Grade 3 ($<50-25 \times 10^9/L$)	
First occurrence	Dose interruption until platelets count is $\geq 75,000$, then resume and reduce by one dose level.
Second occurrence	Dose interruption until the platelet count is $\geq 75,000$, then resume and reduce by one dose level.
Third Occurrence	Discontinue onapristone and continue fulvestrant at the discretion of treating physician.
Grade 4 ($< 25 \times 10^9/L$)	Discontinue onapristone and continue fulvestrant at the discretion of treating physician.
Laboratory	
Serum creatinine	
Grade 1 ($\leq 1.5 \times ULN$)	Maintain dose level.
Grade 2 ($>1.5-3 \times ULN$)	Hold, evaluate for other causes. If the workup is negative, and creatinine resolved to $\leq 1.5 \times ULN$ within 14 days, resume and consider maintaining the dose level but may reduce by one dose level.
Grade 3 ($>3.0-6.0 \times ULN$)	Hold, evaluate for other causes. If related to onapristone, then permanent discontinuation of treatment. If not related, and the creatinine level improves to $\leq 1.5 \times ULN$ within 14 days, then resume at same dose level. If renal dysfunction is related to onapristone and or >14 days required for recovery, then discontinue onapristone and continue fulvestrant at the discretion of the treating physician.
Grade 4 ($>6.0 \times ULN$)	Hold, evaluate for other causes. If related to onapristone, then permanent discontinuation of treatment. If not related, and the creatinine level improves to $\leq 1.5 \times ULN$ within 14 days, then resume at same dose level. If renal dysfunction is related to onapristone and or >14 days required for recovery, then discontinue onapristone and continue fulvestrant at the discretion of the treating physician.
Total bilirubin**	
Grade 1 ($> ULN - 1.5 \times ULN$)	Maintain dose level.

Adverse event	Dose of Onapristone
Grade 2 ($> 1.5\text{--}3.0 \times \text{ULN}$)	
Dose interruption. Evaluate for other causes, and repeat LFT every week until resolved to $\leq 1.5 \times \text{ULN}$.
 
 – If resolved in ≤ 14 days, maintain dose level. – If resolved in >14 days, then resume and reduce by one dose level.
Grade 3 ($> 3.0\text{--}10.0 \times \text{ULN}$) **	
Dose interruption. Evaluate for other causes, and repeat LFT every 72 hours until resolved to $\leq 1.5 \times \text{ULN}$.
 
 – If resolved in ≤ 14 days, then resume and reduce by two dose levels – If resolved in >14 days, discontinue onapristone and continue fulvestrant at the discretion of treating physician.
Grade 4 ($> 10.0 \times \text{ULN}$) **	Discontinue onapristone and continue fulvestrant at the discretion of treating physician.
Liver function tests (ALT or AST)	
Grade 1 ($> \text{ULN} - 3.0 \times \text{ULN}$)	Maintain dose level.
Grade 2 ($> 3.0\text{--}5.0 \times \text{ULN}$)	
Dose interrupt, and evaluate for other causes, and repeat LFT every week until resolved to $\leq 3.0 \times \text{ULN}$.
 
 If resolved in ≤ 14 days, maintain dose level. If resolved in >14 days, then resume and reduce by one dose level
Grade 3 ($> 5.0\text{--}20.0 \times \text{ULN}$)	
Dose interruption. Repeat LFT every 72 hours until resolved to $<$ or equal to grade 1 value.
 
 – If resolved in ≤ 14 days, then resume and reduce by one dose level. – If resolved in >14 days, may resume with reducing two dose levels and monitoring of LFTs twice a week for the first week and then weekly for four weeks (then return to study calendar).
Grade 4 ($> 20.0 \times \text{ULN}$)	Discontinue onapristone and continue fulvestrant at the discretion of treating physician.
Hy's Law Criteria	
Grade ≥ 2 bilirubin in conjunction with grade ≥ 2 transaminase and without elevation of alkaline phosphatase)	Discontinue onapristone and continue fulvestrant at the discretion of treating physician.
Other non-hematological toxicity***	
Grade 1	Maintain current dose.
Grade 2	Continue unless intolerable despite optimal medical management, then dose interruption. Monitor toxicity until resolved to grade 1 or tolerable grade 2. If grade 2 event was tolerable to subject, the study treatment could continue under the supervision of the treating provider.

Adverse event	Dose of Onapristone
	
 – If resolved in ≤14 days, maintain dose level. – If resolved in >14 days, then resume and reduce by one dose level.
Grade 3	
Dose interruption. Monitor toxicity until resolved to grade 1 or better.
 
First Occurrence
 
 – If resolved in ≤14 days, maintain dose level. – If resolved in >14 days, then resume and reduce by one dose level. 
Second Occurrence
 
Dose interruption. Monitor toxicity until resolved to grade 1 or better.
 
 – If resolved in ≤14 days, maintain dose level. – If resolved in >14 days, discontinue onapristone and continue fulvestrant at the discretion of treating physician. 
Third Occurrence
 
 - Discontinue onapristone and continue fulvestrant at the discretion of treating physician.
Grade 4	Discontinue onapristone and continue fulvestrant at the discretion of treating physician.

*No dose modifications planned for other hematologic parameters (i.e., lymphocytes).

**For patients with Gilbert Syndrome, these dose modifications apply to changes in direct bilirubin only.

***Dose modifications for nausea, vomiting, diarrhea or electrolyte abnormalities only required if toxicity lasts longer than 48 hours despite maximal medical therapy. Treating providers may choose to evaluate subjects with pertinent labs for further evaluation (for fatigue, only if toxicity lasts longer than seven days despite maximal medical therapy).

Potential for Drug-Drug Interaction

In vitro, onapristone is a reversible as well as a time-dependent inhibitor of CYP3A4 and showed potential for CYP3A4 induction. Therefore, until more data are available, patients should be advised to avoid those agents which are sensitive substrates or strong inducers or inhibitors of CYP3A4 (see Table 6).

Inhibitors of CYP3A4: Coadministration with strong inhibitors of CYP3A4 should be avoided. Coadministration with moderate CYP3A4 inhibitors should be used in caution. Seville orange, star fruit, grapefruit and their juices affect P450. Concomitant use should be avoided.

Inducers of CYP3A4: Avoid the use of strong CYP3A4 inducers. If patients require coadministration of strong CYP3A4 inducers (i.e., phenytoin, carbamazepine, rifampin, rifabutin, phenobarbital, St. John's wort), treating providers and the designated pharmacists are required to monitor patients' labs given that there are no clinical data to guide dose adjustment for onapristone in patients receiving strong CYP3A4 inducers or inhibitors.

Table 6: Clinically relevant drug interactions: inducers and inhibitors of isoenzyme CYP3A. Treating providers may choose to use the reference link below for drug interactions.

Inducers
Barbiturates, carbamazepine, enzalutamide, glucocorticoids, modafinil, oxcarbazepine, phenobarbital, phenytoin, pioglitazone, rifabutin, rifampin, St. John's wort, troglitazone, efavirenz, nevirapine.
Strong inhibitors
Clarithromycin, indinavir, itraconazole, ketoconazole, nefazodone, neflifinavir, ritonavir, saquinavir, telithromycin.
Moderate inhibitors
Aprepitant, diltiazem, erythromycin, fluconazole, grapefruit juice, verapamil.
Indiana University School of Medicine's Drug Interaction Table (https://drug-interactions.medicine.iu.edu/Main-Table.aspx) (accessed on March 1, 2019)

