7.5.2 Onapristone Identified Safety Risk

In the phase I trial [Cottu 2018], seven patients (13%) experienced transient dose interruptions for AEs (one each: nausea, ALT increase, gastroenteritis, GGT increased, thoracic pain, postprocedural cellulitis, LDH increase, abdominal pain and atrial fibrillation).

Thirty patients (58%) experienced at least one grade 3 or grade 4 adverse event. In 10 patients (19%), the following adverse events were considered related to ONA: increased GGT (13%), increased AST and ALP (6% each), increased bilirubin (4%), and increased ALT and LFTs, asthenia and pulmonary embolism (2% each). All except two of these AEs were associated with progressive disease: one G3 GGT elevation at week 12 in a responding patient, lasting one month with associated transient G1 AST and bilirubin increase, with no clinical symptoms; and the other a G3 GGT elevation at week 3, lasting three weeks, in a patient with liver metastases and baseline G1 GGT elevation. Both elevations decreased spontaneously with no action taken. None of the G3 AST, ALT or bilirubin elevations were considered to be dose limiting by the independent data review committee due to the presence of concurrent progressive disease in the liver.

7.5.3 ^{18}F -FFNP PET/CT Identified Safety Risk

To date, no significant adverse events have been reported as a result of the intravenous administration of ^{18}F -FFNP for PET imaging applications [54].

As with any IV administered agent, ^{18}F -FFNP could cause an allergic reaction that could potentially pose a threat to life (anaphylaxis). This has not been observed in reported human exposure to date. Reasonable precautions should be taken, consistent with normal radiologic and clinical facility practice. The patient should be monitored until the PET procedure is completed, and trained personnel and emergency equipment should be available per facility standards.

For purposes of informed consent regarding reasonably foreseeable risks to subjects in trials utilizing ^{18}F -FFNP, the following potential adverse events are considered:

- Injection-related risks that may include infection, or accidental extravasation of the dose that may lead to discomfort, localized pain, or infection (rare occurrence).
- Risks related to allergic reaction/anaphylaxis that may be life-threatening (extremely rare occurrence).

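### Table 5 tells the investigator both to stop and to resume onapristone after a first or second related febrile neutropenia episode with ANC below 0.5

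*Combined protocol and SAP*

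**What the plan says.** Section 6.2.2 applies dose modification to severe or intolerable reactions that are "at least possibly, probably or definitely related to onapristone" and refers the reader to Tables 4 and 5. Two hematological rows of Table 5 matter here.

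- **Neutropenia, grade 4 (ANC < 0.5 x 10^9/L):** discontinue onapristone; fulvestrant may continue if the treating physician wishes. The row has no occurrence count and no condition about fever.
- **Febrile neutropenia (ANC < 1.0 x 10^9/L plus a temperature criterion):** for a first or second episode, interrupt until ANC is at least 1.0 x 10^9/L; then, "when improved and afebrile, resume and reduce by one dose level". Onapristone is discontinued at the third episode. The row has no lower ANC limit.

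The surrounding text adds several general rules: "A maximum of two dose reductions will be allowed", with discontinuation for events after that; reductions follow the worst preceding toxicity; a delay of more than 28 days ends onapristone; and the physician's clinical judgment "should guide the management plan of each subject based on individual benefit/risk assessment".

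**The concern.** The two rows overlap, and in the overlap their actions are opposite: one ends onapristone, the other restarts it at a lower dose. This is more than a missing detail, because both instructions are written down.

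The febrile row is also out of step with the rest of the table. For onapristone-related events, the grade 4 rows for platelets, bilirubin, ALT/AST, creatinine and other non-hematological toxicity all lead to discontinuation. The febrile row is the only one that offers a way back to dosing after a related grade 4 count, and it offers it to the patient with the added complication of fever.

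What is at stake is the safety and consistency of dosing. At a multi-site trial, two investigators could each follow the table and manage identical patients in opposite ways. One of those patients would be re-exposed to the suspected drug.

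**Working it through.** The plan states no figure on this point, so the main check is to intersect the two rows' entry conditions and compare their actions.

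**Step 1: the overlap.** {ANC < 0.5} and {ANC < 1.0 with fever} intersect in {ANC < 0.5 with fever}, which is not empty. A subject with ANC 0.3 x 10^9/L and fever is an example.

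**Step 2: actions for related events, before two reductions have been used.**

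| Situation | Neutropenia rows | Febrile row | Agree? |
|---|---|---|---|
| ANC 0.5 to < 1.0 with fever, first or second occurrence | Interrupt, resume one level lower | Interrupt, resume one level lower | Yes |
| ANC < 0.5 with fever, first or second episode | Discontinue | Interrupt, resume one level lower | **No** |
| ANC < 0.5 with fever, third episode | Discontinue | Discontinue | Yes |
| ANC < 0.5, no fever | Discontinue | Does not apply | Not applicable |

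The conflict is confined to the second line.

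**Step 3: is there a tie-breaker?**

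- The worst-toxicity sentence is about dose reduction. It does not choose between reducing and discontinuing, and it does not rank fever against a grade 4 count.
- The cap on reductions settles the matter only once both have been used. It does not reach a first episode at the starting dose.
- The 28-day rule is about delay. A count that recovers sooner stays in conflict.
- The hematological footnote covers only other parameters such as lymphocytes. The triple-asterisk footnote covers gastrointestinal, electrolyte and fatigue events.
- The clinical-judgment clause lets the physician decide but does not say which row is the recommendation.

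None of these says which row governs.

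**Step 4: how often could it arise?** Section 6.2.2 reports that onapristone treatment doses in earlier cancer studies "also demonstrated no grade 4 toxicities". Section 7.5.2 lists the related grade 3-4 events of the phase I trial, and neutropenia is not among them. Section 1.4.1.6 gives the size of that trial as 52 patients. Assuming the list is complete, the count of related grade 3-4 neutropenia is 0 of 52.

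- One-sided 95% upper bound: 1 - 0.05^(1/52) = 0.0560; 39 x 0.0560 = 2.18 subjects.
- Upper limit of the two-sided 95% exact interval: 1 - 0.025^(1/52) = 0.0685; 39 x 0.0685 = 2.67 subjects.

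These are upper limits for any related grade 3-4 neutropenia. Febrile episodes with ANC below 0.5 are a subset of that.

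**The case against.** The best reply is that this is unstated precedence and not a true contradiction. The grade 4 row is unconditional, so a reader who applies every row that is met stops onapristone, and there is then nothing left to resume. Table 5 already works this way for Hy's Law: such a case also meets the grade 2 bilirubin and transaminase rows, which allow resumption, yet the discontinue row plainly governs. This makes discontinuation the more natural reading but does not establish it. The Hy's Law row is also the more specific row, and a rule that the specific row governs would here favor the febrile row.

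Three further points stand, and they limit the weight of the finding:

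- Table 5 is guidance. No physician is obliged to resume.
- The febrile row allows resumption only after the count has recovered and the fever has gone, at a lower dose, with no later re-escalation. No reading doses a subject who is still febrile or has not recovered to ANC 1.0 x 10^9/L.
- The figure of 2 of 39 is a confidence bound on a broader event, from a trial of onapristone without fulvestrant in mixed tumor types. It is not an expected count.

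It is also fair to say that the documents do not show which outcome was intended. None of this makes the two written instructions compatible.

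**Conclusion.** The concern holds, as a minor one. For a related first or second febrile episode with ANC below 0.5 x 10^9/L, before two dose reductions have been used, Table 5 gives opposite onapristone instructions and no rule chooses between them. One of them is less protective for a febrile subject than for an afebrile subject with the same count.

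The primary endpoint and the Simon decision boundaries do not depend on it. Any effect on the safety monitoring in section 9.2 is at most indirect: that rule counts discontinuation of the combination, fulvestrant may continue after onapristone stops, and crossing a boundary leads only to a meeting of the principal investigator and study chair.

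The statement that the case is rare rests on the phase I list being complete and on that experience carrying over to the combination with fulvestrant, which the documents do not show. The conflict itself rests on the text alone.

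**What to change.** Change Table 5 in one of two ways:

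- limit the febrile neutropenia row to ANC 0.5 to < 1.0 x 10^9/L; or
- add one sentence: *When two rows apply, the more restrictive one governs.*

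Either change sends ANC < 0.5 with fever to onapristone discontinuation, with fulvestrant at the physician's discretion, in line with the other grade 4 rows for related events. The first option leaves the febrile row close to the grade 3 neutropenia row, with the requirement to be afebrile as the main addition. The second also makes explicit how the Hy's Law row relates to the individual liver rows. If the sponsor does intend resumption after febrile grade 4 neutropenia, that exception should be written into the grade 4 row.

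The cost is one line of text, with no new data, visits or procedures.

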_____ 5. Measurable disease, i.e., at least one measurable lesion, as per RECIST 1.1 criteria. A palpable, and measurable breast mass is acceptable.

_____ 6. ECOG Performance status \leq 2. ECOG PS: _____ Date: _____

_____ 7. Adequate organ function:

- AST, ALT \leq 2.5 times institutional upper limit.

AST: _____ ULN: _____ Date: _____

ALT: _____ ULN: _____ Date: _____

- Total bilirubin \leq 1.5 \times ULN, except for subjects with Gilbert's syndrome who may be included if their total bilirubin is \leq 3.0 \times ULN and direct bilirubin \leq 1.5 \times ULN.

T. Bili: _____ ULN: _____ Date: _____

If subject has Gilbert's syndrome:

D. Bili: _____ ULN: _____ Date: _____

- ALP \leq 2.5 times institutional upper limit with exception that ALP of $< 5 \times$ ULN is acceptable in patients with elevated with ALP due to bone metastases (in the absence of liver metastases).

ALP: _____ ULN: _____ Date: _____

- Serum creatinine $< 1.5 \times$ ULN.

Creatinine: _____ ULN: _____ Date: _____

- Absolute neutrophil count (ANC) $\geq 1000/\mu\text{L}$.

ANC: _____ Date: _____

- Patients with lymphopenia are eligible at the discretion of the treating provider.
- Hemoglobin (Hb) \geq 8g/dL.

Hemoglobin: _____ Date: _____

- Platelet count \geq 100,000/ μ L.

Platelets: _____ Date: _____

_____ 8. Female subjects must meet one of the following:

- Postmenopausal for at least one year before enrollment,
OR
- Surgically sterile (i.e., undergone bilateral oophorectomy),
OR
- Premenopausal is defined as someone who has had menses at any time in the preceding 12 months. Premenopausal women who are eligible for this trial will require a GnRH analogue and treating physician may choose to monitor the ovarian function with laboratory tests (FSH/LH/Estradiol) to ensure a complete menopausal status with cessation of menses.

_____ 9. Women of childbearing potential must have a negative pregnancy test within seven days of registration. Subjects must have a negative pregnancy test seven to 10 days prior to starting study treatment.

Date of negative pregnancy test: _____

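### Table 5's Hy's Law stop for onapristone is conditional on ALP not being elevated, with no baseline reference, although inclusion 7 admits subjects whose ALP is already raised

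*Combined protocol and SAP*

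**What the plan says.** **The combined stop.** The Hy's Law row of Table 5 (section 6.2.2) discontinues onapristone for grade 2 or higher bilirubin together with grade 2 or higher "transaminase and without elevation of alkaline phosphatase". Fulvestrant may continue. Hy's Law is mentioned nowhere else, and no other section says what counts as ALP elevation for this rule.

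**Entry limits.** Inclusion 7 (section 4.2) allows ALP up to 2.5 × ULN. For values below 5 ×, it adds that "ULN is acceptable in patients with elevated with ALP due to bone metastases (in the absence of liver metastases").

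**Single-analyte rows of Table 5**, which govern when the combined row does not apply:
- Bilirubin grade 2: interrupt; same dose if resolved within 14 days, one level lower if later.
- Bilirubin grade 3: if resolved within 14 days, "then resume and reduce by two dose levels"; if later, discontinue.
- ALT/AST grade 2: interrupt; same dose if resolved within 14 days, one level lower if later.
- ALT/AST grade 3: one level lower if resolved within 14 days; if later, the subject "may resume with reducing two dose levels and monitoring of LFTs twice a week for the first week".
- Grade 4 of either: discontinue.

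**General limits in section 6.2.2.** "A maximum of two dose reductions will be allowed". Then: "Any adverse events even after the dose reductions will indicate treatment discontinuation with onapristone". Also: "Dose reduction should be based on the worst preceding toxicity". If a delay exceeds 28 days, "then the subject must be discontinued from onapristone but may continue fulvestrant". Table 4 gives three doses: 50, 40 and 30 mg BID.

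**The concern.** An ALP condition is a legitimate part of a Hy's Law criterion, because raised ALP can point to cholestasis rather than hepatocellular injury. The difficulty is that here the condition can be settled at enrolment by a value unrelated to the liver event.

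The other two limbs do not have this problem. Entry AST and ALT are at most 2.5 × ULN, below the grade 2 cutoff (above 3.0 × ULN). Entry bilirubin is at most 1.5 × ULN, and grade 2 begins above that. Gilbert's syndrome has its own rule: a footnote to Table 5 applies the bilirubin modifications to direct bilirubin only, and inclusion 7 caps direct bilirubin at 1.5 × ULN. So both limbs require worsening on study. ALP has no equivalent provision, although the protocol deliberately admits bone-derived elevation.

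At stake is consistent protection after a combined liver event. Two subjects with the same transaminase and bilirubin values could receive opposite written guidance, one to stop and the other to resume, because of an ALP value one of them already had at entry. Sites could also apply the row differently.

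**Working it through.** The plan gives no figure to reproduce. The check applies its written rules to every combination that the general limits leave open.

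**Inputs (Table 5).** Dose levels to drop after recovery:
- ALT/AST: grade 2 in ≤14 days, 0; grade 2 in 15–28 days, 1; grade 3 in ≤14 days, 1; grade 3 in 15–28 days, 2 (permissive wording).
- Bilirubin: grade 2 in ≤14 days, 0; grade 2 in 15–28 days, 1; grade 3 in ≤14 days, 2; grade 3 in 15–28 days, discontinue.

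Each analyte has 2 grades × 2 recovery windows = 4 states. Letting the two recover independently gives 4 × 4 = 16 combinations. Grade 4 values and delays beyond 28 days are left out because they stop the drug at any ALP.

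**Rule.** Levels to drop = the larger of the two entries, since the worst toxicity governs. Resume dose = current dose − 10 mg × levels. Stop if either row says discontinue, if the drop would go below 30 mg BID, or if the subject is already at 30 mg BID.

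**ALP normal.** The Hy's Law row applies: stop in 16 of 16.

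**ALP above ULN, read literally, event at 50 mg BID** (resume dose, mg BID):

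| ALT/AST | Bili G2 ≤14 d | Bili G2 15–28 d | Bili G3 ≤14 d | Bili G3 15–28 d |
|---|---|---|---|---|
| G2 ≤14 d | 50 | 40 | 30 | stop |
| G2 15–28 d | 40 | 40 | 30 | stop |
| G3 ≤14 d | 40 | 40 | 30 | stop |
| G3 15–28 d | 30 (may) | 30 (may) | 30 (may) | stop |

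Resume: 4 × 3 = 12 of 16. In 3 of these the text permits resumption rather than directing it.

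**At 40 mg BID**, one level remains. Resumption needs an ALT/AST entry of 0 or 1 (3 states) and a bilirubin entry of 0 or 1 (2 states): 3 × 2 = 6 of 16.

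**At 30 mg BID**, any further event stops the drug: 0 of 16.

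**Example.** First event at 50 mg BID, ALT 4 × ULN (grade 2) and bilirubin 2 × ULN (grade 2), both resolved by day 10. With normal ALP: discontinue. With a stable, bone-derived ALP of 2.0 × ULN: both rows give 0 levels, so resume at 50 mg BID.

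**How many subjects.** This cannot be computed. Section 7.5.2 reports related grade 3/4 events in phase I (bilirubin 4%, ALT 2%, AST and ALP 6% each), but no grade 2 rate, no rate of combined events and no distribution of baseline ALP.

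**The case against.** The strongest reply is that the gap exists only under one reading. The first column of Table 5 is headed as adverse events, and section 6.2.2 applies the table to reactions at least possibly related to onapristone. A stable entry ALP is neither, so elevation could mean an on-treatment rise. Sections 1.4.1.6 and 7.5.2 do separate baseline from on-treatment liver abnormalities. The row also ends in an unmatched bracket, so leaning on its exact letter is uncomfortable. This much stands: the on-treatment reading is available and would close the gap. But the row does not state it, and inclusion 7 itself applies the word elevated to an entry value.

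Second, Table 5 is offered as recommendations under clinical judgment. The grade 2–3 bilirubin rows and the grade 2 ALT/AST row call for a search for other causes. Investigators may withdraw a subject (section 5.3.2), the disease team discusses toxicities and dose adjustments (section 11.2), and the DSMC chair reviews every SAE in real time (section 11.6). These are real safeguards. They permit a stop; none requires one or defines ALP elevation.

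Third, the counts carry no probability and the affected group is probably small. That stands in full. Section 7.5.2 adds that all but two of the related grade 3/4 events accompanied progressive disease.

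A reader might infer that raised ALP switches off liver stopping altogether, or that the protocol obliges rechallenge. Neither follows. Grade 4 values, grade 3 bilirubin unresolved at 14 days, a delay beyond 28 days and any event after two reductions stop onapristone at any ALP, and a clinician may always stop.

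**Conclusion.** The point holds as a gap in the wording of a safety rule. Read literally, a stable, non-hepatic ALP elevation that the protocol accepts at entry removes the mandatory combined stop. The remaining rows then allow resumption in 12 of 16 combinations at 50 mg BID, 6 of 16 at 40 mg and 0 of 16 at 30 mg, against a stop in all 16 when ALP is normal. The combinations are not equally likely.

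The counts assume that elevation means above ULN; that the two analytes recover independently, both within 28 days; that the delay equals the longer recovery time; that the larger reduction governs; that a drop below 30 mg BID means stop; and that a subject at 30 mg BID has used both reductions.

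It would be wrong to conclude that the ALP condition should be deleted, since only its missing baseline reference is at fault. Nor does the gap bear on the response-rate endpoint or the two-stage decision rule in section 9.2. It is a cheap improvement for patient safety.

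**What to change.** Reword the row so that onapristone stops for grade ≥2 bilirubin plus grade ≥2 transaminase unless there is a new on-treatment rise in ALP. Define that rise as above ULN if baseline ALP was normal, or at least 2 × baseline if baseline ALP was above ULN.

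The factor of 2 is an assumption for the clinical team to confirm. It should be clearly above 1, for example 1.5 to 2. It is tempting to say that any factor above 1 would do, but that is true only for an exactly unchanged value: drift from 2.0 to 2.2 × ULN is a ratio of 2.2 / 2.0 = 1.1, which would remove the stop at a factor of 1.05 but not at 1.5 or 2. For a baseline of 2.5 × ULN, a factor of 1.5 sets the cutoff at 3.75 × ULN and a factor of 2 at 5.0 × ULN.

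The rewording does not settle everything. An ALP rise from bone progression, or a normal baseline drifting just over ULN, would still lift the mandatory stop and remains a matter for clinical judgment, as under the literal reading now.

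The cost is one table row. No new tests are needed: baseline ALP is on the eligibility checklist (section 4.2), and ALP, ALT, AST and total bilirubin are in the chemistry panel (section 10.3, Table 8). The downside is possibly a few more onapristone discontinuations, with fulvestrant still allowed.
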